15.1.4. Sensitivity analysis

Sensitivity analysis will test the robustness of the results. Key parameters will be varied to determine the impact of changes on results. Non-parametric bootstrapping and probabilistic sensitivity analysis will be undertaken to explore uncertainty in the confidence to be placed on the results of the economic analysis and cost-effectiveness acceptability curves presented.

Pre-specified sensitivity analyses are as follows:

- Cost per hernia clinically detected at 2 years
- Cost per additional quality adjusted life (QALY) year gained at 2 years
- Alternative costs of the intervention

Data (costs and effects) will be analysed as:

- Complete case analysis, where only participants with complete data are included. This will be the base case analysis.
- multiple imputation, where all study participants are included (imputed values will be used for missing costs and effects)

15.2. Model-based cost-effectiveness analysis

The model-based economic evaluation will estimate the long-term cost-effectiveness of using collagen tissue matrix for patients undergoing elective closures of stomas. It is anticipated a mathematical model will be constructed to determine the long-term (beyond 24 months) costs and outcomes associated with either collagen tissue matrix or usual closure of stoma sites. The model will be developed using TreeAge Pro Suite 2015 software (TreeAge Software Inc, Williamstown, MA, USA).

The model structure will be informed by reviewing modelling studies that have been undertaken which consider long-term outcomes associated with incision hernias or outcomes after stoma closures and by expert opinion within the team. Costs in the model will include those for the collagen tissue matrix pathway and usual closure techniques derived from the trial-based analysis, re-admissions, re-operations and long-term hernia. Outcomes will be in the form of survival and quality of life (if available) and will use data collected from the trial and literature on quality of life after a hernia/stoma.

The model will be run over remaining lifetime, with costs and benefits discounted at a rate of 3.5%. The incremental cost-utility analysis will be conducted from an NHS and Personal Social Services (PSS) perspective. Extensive deterministic sensitivity analysis will be undertaken to assess the impact of changing the values of key parameters. For each important model parameter, we will determine a point estimate and construct a probability distribution around the estimate. Probabilistic sensitivity analyses will be conducted to deal with uncertainty in model parameters and cost-acceptability curves presented.

16.Organisation

ROCSS

To ensure the smooth running of ROCSS and to minimise the overall procedural workload, it is proposed that each centre should designate individuals who would be chiefly responsible for local coordination of the surgical and administrative aspects of ROCSS. The ROCSS Trial Office will provide as much assistance as they can to local co-ordinators and investigators in obtaining Trust approval in each centre and helping resolve any local problems that may be encountered.

16.1. Funding

The ROCSS feasibility study was funded by an unconditional educational grant from LifeCell.

Follow-up and analysis of the phase II trial has been funded by the NIHR Research for Patient Benefit Programme.

The study has been adopted to the NIHR Clinical Research Network portfolio. This will have benefits in coordination of research efforts, dissemination of trial information and local support for investigators.

16.2. Principal Investigator at each Centre

Each ROCSS centre should nominate a Consultant Colorectal Surgeon to act as the local Principal Investigator (PI) and bear responsibility for the conduct of research at their centre. The responsibilities of the local PI will be to ensure that all medical and nursing staff involved in the care of potential patients are well informed about the trial and trained in trial procedures, including obtaining informed consent. Close collaboration between all clinical teams is particularly important in order that patients for whom the ROCSS trial is an option can be identified sufficiently early for entry into the trial.

The local PI will also be responsible for ensuring standardisation of the technique for reinforcement with the collagen mesh. The local PI should liaise with the Trial Coordinator on logistic and administrative matters connected with the trial.

16.3. Radiologist at each Centre

It is suggested that each ROCSS centre should nominate a Consultant Radiologist as Local Radiology Coordinator. This person will be responsible for ensuring that the 12-month CT scan is carried out to protocol for all ROCSS patients when requested to do so by local clinicians and to provide these scans for centralised study evaluation. The nominated radiologist will be sent updates and newsletters and will be invited to ROCSS progress and training meetings.

16.4. Central Coordination

The Trial Office at the BCTU is responsible for providing the following trial materials:

- The Site File, including all regulatory documentation required to define the involvement of the centre in the trial and printed patient materials, such as participant information sheets, consent forms and GP letters.
- An online randomisation system, including individual log-in and passwords and guidance will be supplied to each collaborating centre, after relevant authorisations have been obtained.

Additional supplies of any printed material can be obtained on request. The Trial Office also provides the central randomisation service and is responsible for collection and checking of data and for reporting of serious adverse events to the sponsor and regulatory authorities on behalf of the Chief Investigator and for any interim and final data analyses. The Trial Office will help resolve any local problems that may be encountered in trial participation.

16.5. Clinical Queries

During office hours, the clinical coordinators (see inside front cover for contact details) provide an oncall service for any clinical queries about the trial.

16.6. Strattice® Collagen Mesh Supply

The Strattice® collagen mesh to be used within the trial will be provided free of charge from Lifecell. Only one collagen mesh per patient randomised to receive it will be supplied free of charge. One dedicated mesh will be delivered to each site upon opening. When this mesh has been used, a reorder form can be faxed to LifeCell who will re-supply within 24 hours for orders placed Monday – Thursday.

16.7. CT scans

For the main phase of the trial, hospital trusts will be reimbursed for the follow-up CT scan performed at 12-months post-randomisation for those patients who would not normally undergo a scan at this time (ie colorectal cancer patients in the UK who would normally have a CT scan at one year would not be reimbursed for the cost of this scan). Reimbursement will be via an invoice to the ROCSS Study Office. Detailed information about pathways for sending CT scans back to the central office for interpretation will be provided on a site by site basis by the ROCSS Study Office. For hospitals with PACS links, there will be provision for anonymised electronic transfer. For centres without these links, there will be provision for secure postage of a CD back to the ROCSS Trial Office at the BCTU.

Inclusion of patients in the ROCSS trial should therefore incur only minimal additional costs for participating hospitals. Follow-up appointments can be co-ordinated to fit in with the patient's existing follow-up schedule.

16.8. Patient and Public Involvement

IA (the ileostomy and internal pouch support group) is a UK registered charity whose primary aim is to help people who have to undergo surgery that involves the removal of their colon (known as a colectomy) and the creation of either an ileostomy or an ileo-anal pouch (http://www.iasupport.org/). It was started in 1956 by a group of people who had ileostomies themselves, together with some members of the medical profession. It was the first ostomy association in the United Kingdom and it is a registered national charity (no. 234472).

The IA has 55 local groups throughout Great Britain and Ireland and represents the widest possible representation of our sample group for adequate Patient and Public Involvement. At an early stage, the protocol was submitted to the IA's research sub-committee for feedback and approval. After some minor changes, particularly to the patient information sheet, the National Secretary of the IA confirmed their support for the trial and protocol.

16.9. Publication and Dissemination of Results

A meeting will be held at the end of the trial to allow discussion of the main results among the collaborators prior to publication. The success of the trial depends entirely on the wholehearted collaboration of a large number of doctors, nurses and researchers. For this reason, chief credit for the main results will be given not to the committees or central organisers, but to all those who have collaborated in the trial. A writing committee will be convened to produce publications on behalf of the trial collaborators. Centres will not be permitted to publish data obtained from participants in the ROCSS trial that uses trial outcome measures without discussion with the Chief Investigator and the Trial Steering Committee.

It is envisaged that the results from the ROCSS trial will be:

- Used to make recommendations to commissioners about the routine use of prophylactic reinforcement of closure of stoma sites, through the Nice Institute of Clinical Excellence (NICE) guideline structure
- Reported to the Ileostomy Association in order to inform their members and for dissemination to the general public
- Published in a peer reviewed, high impact surgical journal
- Presented at regional, national and international conferences

17.Research Governance

The conduct of the trial will be in accordance with the principles of the International Committee on Harmonisation of Good Clinical Practice Guidelines and the Research Governance Framework for Health and Social Care plus any subsequent amendments.

17.1. Sponsor

National sponsorship will be provided by the University of Birmingham upon signing of the Clinical Study Site Agreement with each trial site.

17.2. Clinical Trials Unit

Data from this trial will be handled by the BCTU at the University of Birmingham. BCTU is a full-time research facility dedicated to, and with substantial experience in, the design and conduct of randomised clinical trials. The BCTU recognises the responsibilities of a data management centre with respect to the ethical practice of research and the adequate protection of human subjects.

17.3. Confidentiality of Personal Data

The trial will collect personal data about participants, and medical records will be reviewed for all patients and routine physical examinations will be performed. Participants will be informed that their trial data and information will be securely stored at the trial office at the BCTU, and will be asked to consent to this. The BCTU abides by the UK law Data Protection Act 2018. The data will be stored on a secure computer database, and all personal information obtained for the study will be held securely and treated as strictly confidential. Any data processed outside of the BCTU will be anonymised.

17.4. Long-Term Storage of Data

In line with Good Clinical Practice guidelines, all essential documentation and data will be retained for at least 10 years.

17.5. Indemnity

ROCSS was developed by the West Midlands Research Collaborative and the BCTU, and the feasibility study is being supported by Lifecell. The University of Birmingham is the trial 'sponsor.' The normal NHS indemnity liability arrangements for clinician-initiated research will, therefore, operate – see NHS Executive Health Service Guidelines HSG (96) 48, 8th November 1996. It should be noted, however, that negligent liability remains the responsibility of the hospital, whether or not a patient is part of a clinical trial, because of the duty of care that the hospital has for their patients.

18.Results from the ROCSS trial

The ROCSS trial was published in *The Lancet* in February 2020¹⁵. Of 1,286 patients screened, 790 were randomised, 394 to mesh closure and 396 to standard closure. The clinically detectable hernia rate at 2 years was significantly lower in the mesh group (12% vs 20%, RR 0.62, 95% Cl 0.43 - 0.90, p=0.012). At 1-year there was a lower incidence of radiological hernia in those receiving mesh compared to standard treatment (RR 0.42, 95%Cl 0.26 – 0.69, p<.001). Despite this, no benefit was seen in the rates of symptomatic hernia, surgical reintervention, wound infection, seroma, quality of life, pain scores or serious adverse events.

To investigate the long-term impact of mesh use in stoma closure on quality of life and cost effectiveness ROCSS - Extended Follow-up (ROCSS-EX) has been funded by the NIHR RfPB.

19.ROCSS-Extended Follow-up (ROCSS-EX)

19.1. Research Question

Is there a significant improvement in long-term quality of life for patients that have a biological mesh reinforcement of the abdominal wall at the time of closure of stoma site, and is the intervention cost-effective?

19.2. Aims

ROCSS

1. To investigate if the biological mesh closure group has a significant long-term improvement in participant quality of life 5-8 years after stoma reversal.

2. To determine if the intervention is cost-effective after 5-8 years.

19.3. Objectives

- To assess the long-term effects of mesh reinforcement of the abdominal wall at the time of stoma closure on quality of life
- To assess the participant reported incisional hernia rate
- To report the number of hernia related hospital visits
- To report the number of interventional procedures related to the stoma closure site or any subsequent hernia
- To explore the long-term cost effectiveness of mesh reinforcement

19.4. Outcome measures

Primary:

Quality of life at 5 to 8 years following closure of stoma site comparing participants who had mesh reinforcement of their abdominal wall with participants that had a standard closure. This will be assessed using the HerQLes tool^{17,18}.

Secondary: (all at 5-8 years follow-up)

- Participant reported incisional hernia rate
- Number of hospital visits for any hernia related reason
- Number of interventional procedures related to the stoma closure site or hernia
- Longitudinal QoL assessed using EQ-5D
- Cost analysis for all additional hernia related events

19.5. Inclusion criteria

All participants included in ROCSS are eligible to be included in ROCSS-EX unless they withdrew or did not have their stoma reversed during the duration of the original trial. For those participants who have died, only routinely collected data will be used.

19.6. Sites

All of the UK sites from the original ROCSS trial will be eligible to participate in ROCSS-EX. The two international sites will not participate in ROCSS-EX.

19.7. Choice of QoL measures

A hernia-related quality of life measure will be included to provide more hernia specific information that will allow a better measure of the impact both to the patient and also to inform the cost-effectiveness analysis. The HerQLes tool was specifically designed to evaluate QoL in patients undergoing abdominal wall repair^{17,18}, such as a stoma closure. It contains 12 items, and can be used

both before and after surgery, focusing on abdominal wall function. Each of the 12 questions relate to the patient's abdominal wall function which means that it will be relevant to patients with and without a hernia (such as the ROCSS participant population). It will therefore be possible to use the same tool in both groups i.e. those who had mesh at the time of stoma closure and those who did not, and for participants with and without a hernia.

The HerQLes quality of life survey was not available when ROCSS was developed and so was not used for the original trial. Therefore, we do not have before and after scores to compare. However, the scores can be compared across groups of participants and it is known (from the original ROCSS data and our follow-up data) whether participants have had mesh inserted at the time of stoma closure and whether or not they have or have had a hernia. These groups will provide us with various comparisons to make and so the following exploratory analyses will be investigated limited to the primary outcome;

- Comparison within the control group (no mesh) for those who have developed a clinical or radiological hernia during the follow up period to those without a hernia. This will show the effect that having an incisional hernia has on a participant's quality of life.
- Comparison between the control group and the mesh group for those who did not develop a clinical or radiological hernia during the follow up period. This will show us if inserting a mesh in itself has any effect on quality of life. This has become an even more important comparison with the recent concern regarding mesh use.
- Comparison between the control group and the mesh group for those who have gone onto develop a clinical or radiological hernia. This will show us if developing a hernia despite having a prophylactic mesh inserted has a different effect on quality of life.

The ROCSS trial originally used a non-specific QoL measure (EQ-5D). This will be repeated but evaluated as a secondary endpoint to look at longitudinal impact and provide QALY data.

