7.4. Randomisation Method

Participants will be randomised into the ROCSS trial in a 1:1 ratio of mesh reinforcement to control (standard closure without mesh). A 'minimisation' procedure using a computer-based algorithm will be used to avoid chance imbalances in important prognostic variables.

The minimisation variables will be:

- 1. Stoma type ileostomy versus colostomy.
- If stoma involves an ileostomy and colostomy, it will be stratified into the colostomy group as the current literature shows that colostomies are at a higher risk of hernia than ileostomy¹¹.
- 2. Surgical incision reopening of midline wound or stoma site only.
- 3. Skin closure type primary or secondary.

8. Treatment and Follow-Up

Please see Appendix B for a detailed patient pathway for the day of surgery.

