8.5. Compatibility with Other Studies

Patients in other colorectal cancer trials are eligible for ROCSS if the other trial does not deal with surgical technique. ROCSS would not be compatible with neo-adjuvant colorectal cancer trials such as FOxTROT. Patients where there is potential conflict should only be approached to enter the ROCSS trial after discussion with the Trial Management Group via the ROCSS Trial Office.

9. Assessment Schedule

ROCSS

Both the patient and the medical and nursing staff responsible for the follow-up assessments will be blinded as to whether or not the stoma closure has been reinforced with collagen mesh.

Trial data will be recorded by hospital research staff on the Case Report Forms (CRFs) and submitted to the ROCSS Trial Office at the BCTU. The patient's unique trial number, initials, hospital number and date of birth will be recorded on all proformas.

Data will be collected at patient entry, intraoperatively, 30-days post-operatively and at 12 and 24 months post randomisation. This is summarised in the table below.

	Prior to patient entry/ Day of admission for surgery	At surgery	30 days post-op +/-5 days	12 months +/- 3 m	24 months +/- 1 m
Informed consent					
Clinical examination			V	\checkmark	
Pre-operative assessment data	\checkmark				
Operative details					
Clinical follow-up				\checkmark	\checkmark
Complications			V	\checkmark	\checkmark
Re-interventions			V		\checkmark
Resource usage (Cost collection)				\checkmark	
Quality of Life & Pain Measures			\checkmark		
CT scan					

At the time of patient entry into the trial, the following data will be collected:

- Demographics (age, gender, BMI, primary indication for stoma, when stoma was formed, diabetes, steroid medication)
- Type of stoma to be closed (ileostomy, colostomy)
- Parastomal hernia
- Incisional midline hernia from primary surgery
- Quality of life forms and pain visual analogue scale.

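### Section 19.7 presents an exploratory, non-randomised comparison of controls with and without a hernia as showing a causal effect on quality of life; it can only estimate an association

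*Protocol*

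**What the plan says.** Protocol section 19.7 explains that HerQLes was not used in the original trial: "Therefore, we do not have before and after scores to compare". In place of change scores it proposes comparisons between groups of participants, introduced with the words "the following exploratory analyses will be investigated limited to the primary outcome". The first is a "Comparison within the control group (no mesh) for those who have developed a clinical or radiological hernia during the follow up period", set against controls without a hernia. The protocol then says what this will deliver: "This will show the effect that having an incisional hernia has on" quality of life. Section 19.7 attaches no caveat about confounding to that sentence and mentions no adjustment.

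Three other places bear on it:

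- Section 7.4 sets out what was randomised: "Participants will be randomised into the ROCSS trial in a 1:1 ratio of mesh reinforcement to control (standard closure without mesh". In explaining how mixed stomas are classified, it also says that "colostomies are at a higher risk of hernia than ileostomy".
- Section 9 lists the data taken at entry, including "Demographics (age, gender, BMI, primary indication for stoma, when stoma was formed, diabetes, steroid medication", together with stoma type, parastomal hernia, and the quality-of-life and pain forms.
- Section 19.11 promises a linear regression with an adjusted mean difference for HerQLes, within an outline of intention-to-treat analyses between arms. It names no covariates and leaves fuller detail to a separate SAP.

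**The concern.** Randomisation balances the mesh and control arms. It does nothing for a split made inside one arm by an event that happens later. Controls who herniate may differ from those who do not in ways that also bear on abdominal-wall function, and the protocol itself names one factor, stoma type, as related to hernia risk. With no earlier HerQLes score, a difference in HerQLes that existed before the hernia cannot be measured directly.

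The comparison is still worth making. The trouble is the conclusion fixed for it in advance: a difference between the groups is to be taken as the effect of the hernia. The original trial found no quality-of-life benefit from mesh, and the extension was set up to look at quality of life again. A sentence promising the effect of a hernia on quality of life is therefore likely to be carried into the report, where patient risk factors could be read as harm from the hernia.

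**Working it through.** **The plan's own figure.** Section 19.11 claims over 85% power for 0.25 SD and over 95% for 0.3 SD with 293 and 295 participants.

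- SE = √(1/293 + 1/295) = 0.0825 SD.
- Power at 0.25 SD: Φ(0.25/0.0825 − 1.96) = 85.8%.
- Power at 0.3 SD: Φ(0.3/0.0825 − 1.96) = 95.3%.

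Both reproduce. They belong to the randomised comparison. The protocol gives no figure for the hernia-versus-no-hernia contrast.

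**Size of the within-control contrast (illustration).** The 295 controls come from section 19.11. The hernia share is assumed to be 20%, the 2-year clinical rate in the Protocol Summary (64 of 327). The planned definition is clinical or radiological over a longer period, so the true split will differ.

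- 0.20 × 295 = 59 with a hernia, 236 without.
- SE = √(1/59 + 1/236) = 0.146 SD, taking SD = 1 in both groups.

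**Spurious difference from one unadjusted factor.** Suppose a hernia has no effect at all. Take obesity as the factor. Its prevalence p (25-30%), its hernia risk ratio RR (1.5-2.5) and its HerQLes effect g (0.3-0.5 SD lower) are all assumptions; the protocol supplies none of them. With hernia share h:

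- P(obese | hernia) = p·RR / (p·RR + 1 − p)
- P(obese | no hernia) = (p − h·P(obese | hernia)) / (1 − h)
- spurious difference = g × (first − second)

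| p | RR | g | obese, hernia | obese, no hernia | spurious difference |
|---|---|---|---|---|---|
| 0.25 | 1.5 | 0.3 | 0.333 | 0.229 | 0.03 SD |
| 0.30 | 2.0 | 0.5 | 0.462 | 0.260 | 0.10 SD |
| 0.30 | 2.5 | 0.5 | 0.517 | 0.246 | 0.14 SD |

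The largest value is just under one standard error (0.136/0.146 = 0.93). The chance of p<0.05 with no true effect is Φ(b/SE − 1.96) + Φ(−b/SE − 1.96), where b is the spurious difference. It is about 5.5% in the first row, 11% in the second and 15% in the third, against a nominal 5%.

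**If more controls have a hernia.** Assume h = 30%, giving 88 and 207 participants.

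- SE = √(1/88 + 1/207) = 0.127 SD.
- First row: 0.3 × (0.333 − 0.214) = 0.04 SD.
- Third row: 0.5 × (0.517 − 0.207) = 0.16 SD.

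The order of magnitude is the same, though the upper end is now somewhat above one standard error.

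**Does section 19.11 already cover it?** Its adjusted mean difference is described for analyses by intervention arm, under intention to treat. It does not say that the same model, or any adjustment, applies to the split by hernia status in section 19.7. Even if it did, an adjusted observational contrast still would not show an effect in the sense that section 19.7 claims.

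**The case against.** The strongest reply is that section 19.7 calls these analyses exploratory, openly says there are no before-and-after scores, and that the covariate list for an exploratory regression is normally SAP material. All of that stands. It lowers the severity, and it means that the missing list is not itself the error. It does not rescue the sentence at issue: the label speaks to how firm the evidence is and does not turn an observational contrast into a causal one. By comparison, section 13.2 says the main trial's subgroup results will be read cautiously and as hypothesis generating. Section 19.7 has no such qualifier on its interpretation.

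A reader might infer three stronger points, and the documents support none of them.

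- *That the comparison must overstate the harm of a hernia, because heavier or sicker patients herniate more and score worse.* The protocol lists BMI, diabetes and steroids only as data collected and says nothing about their relation to HerQLes. The direction is unknown.
- *That the case for mesh is biased.* The mesh question rests on the randomised HerQLes comparison (sections 19.4 and 19.11) and on economic analyses by arm (section 19.12). No stated decision uses the hernia-versus-no-hernia contrast.
- *That a pre-existing difference can be neither seen nor removed.* Baseline HerQLes is missing, but baseline EQ-5D, pain and clinical factors were collected, so imbalance can be examined and partly adjusted for.

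It is also fair to object that the illustration rests on assumed inputs, and that 0.25 SD is the target of a different contrast and so not a yardstick for this one.

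**Conclusion.** The point holds as a fault of interpretation with an inexpensive analytic remedy. Followed as written, section 19.7 would report a non-randomised contrast, defined by an event after randomisation, as the effect of a hernia on quality of life. What it estimates is an association that could partly reflect patient risk factors.

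How large that part is, and in which direction it runs, cannot be derived from the protocol. The illustrative 0.03-0.14 SD depends on the assumed 20% hernia share, on the assumed obesity prevalence, risk ratio and HerQLes effect, and on obesity being the only factor considered. It shows that the issue could matter at the scale of the comparison's own standard error and no more than that. The conclusion does not depend on these numbers, since it follows from what was and was not randomised. Severity is minor to moderate.

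**What to change.** In section 19.7:

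1. Replace the claim that the control-arm comparison will show the effect of a hernia with a statement that it *will estimate the adjusted association* between hernia status and HerQLes.
2. State that the comparison is a linear regression of HerQLes on hernia status among controls, adjusted for pre-randomisation variables already held. Examples are age, sex, BMI, diabetes, steroid use, indication for the stoma, stoma type, parastomal hernia, baseline EQ-5D and baseline pain. Leave the exact list to the SAP, and keep it no longer than the number of hernias can support.
3. Add one sentence naming residual confounding as a limitation, given that there is no baseline HerQLes score.

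The cost is a few lines of protocol text and one regression model. No new data are needed, because the example variables were all scheduled for collection at entry.
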